Subject Payment. The payment schedule is detailed below. Subjects will be paid the medication compliance, study visit bonus, and participation earnings at the end of each experimental day (M, W, F). Subjects will receive an additional bonus (\$50) for completing of the study. Total possible payment for meeting all study requirements and collecting all bonus payments will be \$337.

Medication compliance. \$2 for each metric: 1) Medical Event Monitoring System (MEMS) bottle opening, (2) pill counts (empty bag), (3) positive riboflavin markers, and (4) text reply to reminder. Absence of each will result in payment not being earned for that specific metric. Total possible payment = \$8 per day X 14 study days = **\$112**. **Study visit bonus.** \$10 for on time arrival and providing an alcohol-free breath sample and urine sample. Total possible payment = \$10 per day X 7 visit days = **\$70**.

Participation. Total possible payment = \$15 per day X 7 visit days = **\$105**. **Completion bonus \$50**.

Subject participation requirements. Subjects must take the medication as close as possible to 10:00 PM each evening, and reply “yes” to the medication text prompt (texts will be sent at 15-minute intervals from 9:45 PM to 10:30 PM). On M, W, F over 2 consecutive weeks (see Study Design), subjects will visit the lab at 10 AM. At every visit, they will provide the following: medication update (MEMS bottle), side effects data questionnaire, med check up with nurse, UA fluorescence and toxicology, sleep data (wrist monitor and sleep questionnaire), and stress/anxiety questionnaires. The visit will take approximately 1 hour. In addition, on each Monday (day 1, 7, and 14) subjects will complete: (1) the cold pressor test (with cardiovascular measures and saliva sample for cortisol level), (2) the saccade-based attentional bias test, and (3) the cocaine cue reactivity questionnaire. On these three study days, the visit will take approximately 2 hours.

Data Safety Monitoring Plan

E1. Human Subjects Involvement and Participant Characteristics

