Suvorexant (BELSOMRA) is an orexin receptor antagonist indicated for the treatment of insomnia, characterized by difficulties with sleep onset and sleep maintenance. Recommended dose is 10 mg, 1x per night taken within 30 minutes of going to bed, with at least 7 hours of planned time before awakening. If the 10 mg dose is well tolerated but not optimally effective, it can be increased but not to exceed 20 mg once daily. Medication is taken PO, with dosage in tablets of 5, 10, 15, and 20 mg. Contraindicated in patients with narcolepsy. Precautions include daytime somnolence; dose-related risk of impaired alertness and motor coordination, including impaired driving; patients taking 20 mg should be cautioned against next-day driving; nighttime “sleep-driving” and other complex behaviors while out of bed and/or not fully awake; worsening of depression or suicidal thinking; compromised respiratory function; sleep paralysis, hypnagogic/hypnopompic hallucinations. Risk of the above symptoms increases with use of CNS depressants and alcohol. In obese women (BMI > 30), there is increased risk of exposure-related adverse effects. Belsomra is a schedule-IV compound with mild/modest abuse-potential in the same class as existing sleep medications and anxiolytics. The most common adverse reactions include somnolence and slowed motor coordination. Not recommended for use in patients taking strong CYP3A inhibitors, efficacy may be reduced, or for patients with severe hepatic impairment. Based on animal data, Belsomra may cause fetal harm.

Risks for Behavioral and Psychometric Testing. Behavioral tests are administered via custom written computer programs that track subject’s eye movements. This testing could produce frustration or fatigue if subjects have trouble with acquisition or mastery of the task or concentrating eye gaze for 10-12 minutes. Items on certain psychological/psychiatric questionnaires and interviews might be perceived as personally discomforting to some subjects. While subjects may be uncomfortable reporting these issues, the risks of serious sequelae are extremely low.

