In the event of either an unexpected adverse event or a prolonged period of intoxication, we have several measures in place. First, [name] (CNRA medical director) has clinical experience and training in emergency medicine. Thus, a physician will be in the immediate vicinity of laboratory at all times. Offices and clinical space are within 100 feet of the lab. Collaborating MDs can be paged at any time during the day. Second, Ben Taub Hospital, a level 5 emergency medical center is located just minutes away from BBSB. Finally, in the event of extended sedation, intoxication, or impairment, in which any subject does not appear clear-headed, feeling well, and in full control of his or her behavior, two steps will be taken. First, the subject will remain in the lab until such time that the primary or a co-investigator deems that it is safe for him or her to leave (e.g., passing the sobriety test described above). The large majority of our cocaine use disorder subjects use the METRO system, thus driving hazards are expected to be rare. However, in the event of extended impairment, we will arrange (and pay for) a taxi service to drive the subject back to his/her home rather than having to use METRO. We will administer the Columbia Suicide Severity Rating Scale (CSSRS screening version) at each visit to assess suicidality and depressive symptoms, consistent with current FDA best practices. If the screening indicates change in suicidal ideation, we will administer the full version. If suicidality is judged to clinically significant as per CSSRS scoring criteria, we will (1) report the event to CPHS within 48 hours; (2) remove the patient from the study; (3) make a referral to either the BBSB outpatient mood disorders clinic or UT HCPC, depending on consultation from Dept of Psychiatry outpatient faculty at BBSB.

For the cold pressor task, participants will be told that if the level of pain is too uncomfortable, they should remove the hand immediately and not wait to the end of the 90 sec test period. Each participant will be able to test the water temperature for 10 sec prior to beginning the procedure. These details are presented in the informed consent document. Because there are no sustained effects of cold water, if a participant cannot sustain the immersion for 90 sec on one test day, it will not preclude repeated testing on other lab test days (the cold pressor test will be repeated 3 times).

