Other Protections Against Risk. The following procedures will be taken to safeguard against adverse medication events: (1) careful initial intake evaluation to determine eligibility based on inclusion/exclusion criteria; (2) thorough physical evaluation prior to treatment, consisting of physical examination, standard laboratory tests, electrocardiogram, toxicology screen, pregnancy test, and vital signs; (3) repeated tests during treatment; (4) daily monitoring of pill taking using MEMS caps, returned pill counts, and self-report; (5) weekly review of adverse events and medication compliance; (6) regular evaluation by the study physician ([name]). Specific criteria will be used to exclude potential subjects for whom any of the study medications is contraindicated. Any abnormal physiological, psychological, or behavioral event will be evaluated and, if indicated, will result in the subject's removal from the study.

For all three experiments included in this project, we will use an Adverse Event Log (AEL) based on NIDA SAFTEE procedures. The AEL will record the duration, severity, and frequency or any adverse events, signs, and symptoms. An evaluation will be made as to the event's relationship to the study drug(s), scaled as unrelated, unlikely, possible, and probable. The AEL will be included in the report to DSMB.

Subjects will be monitored regularly for compliance with the study requirements, including the dosing regimen and breath alcohol testing upon arrival at the laboratory each day of testing. Written and verbal information about the medication will be given to all participants. This information will remind the subject to: (1) take food shortly after medication if needed to relieve gastric irritation; (2) inform the treatment research clinic nurse or physician of any over-the-counter and prescription medication taken, especially: cough medication, diarrhea medication, narcotic medication; (2) notify treatment research clinic nurse or physician of any side effects that persist or worsen. The study physician, nurse, and PI will review cases involving clinical deterioration of increased symptomatology or substance abuse. Appropriate actions will be taken, including study termination with proper referral.

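### The medication reminders in E4 do not match the protocol's own description of suvorexant in E3, and the 10 PM dosing rule is not reconciled with E3's bedtime wording

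*Combined protocol and SAP*

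**What the plan says.** **Participant information.** E4, Other Protections Against Risk, says that written and verbal information about the medication will go to all participants, and lists its reminders. The first is "1) take food shortly after medication if needed to relieve gastric irritation". The second is to tell the clinic about any "over-the-counter and prescription medication taken, especially: cough medication, diarrhea medication, narcotic medication". The last is to report side effects that persist or get worse.

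**Drug description.** E3, Potential Risks, lists daytime somnolence, impaired alertness and coordination including driving, complex night-time behaviors, worsening depression or suicidal thinking, respiratory compromise, sleep paralysis and hallucinations. It adds that "patients taking 20 mg should be cautioned against next-day driving" and that "Risk of the above symptoms increases with use of CNS depressants and alcohol". The most common reactions it names are somnolence and slowed motor coordination.

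**Dose and driving.** Study design gives the active arm 10 mg in week 1 and 20 mg in week 2. On driving, E4 (Procedures to Minimize Drug-Related Risks) says that most subjects use public transport, "thus driving hazards are expected to be rare". It provides an impairment check at the end of each experimental day, and a taxi home if impairment is prolonged.

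**Timing.** E3 describes a dose "taken within 30 minutes of going to bed, with at least 7 hours of planned time before awakening". Subject participation requirements states: "Subjects must take the medication as close as possible to 10:00 PM each evening". Study design and the Medication compliance paragraph also use 10 PM. Text prompts run from 9:45 to 10:30 PM, and the text reply is one of four compliance metrics paid at $2 each.

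**The concern.** The E4 list is the only place that states what the medication information will remind participants of. Two of its items, gastric irritation and diarrhea medication, have no source in the protocol's description of the drug. The list also leaves unnamed a caution that E3 itself says patients on the week 2 dose should receive. A site working from E4 could hand out reminders that do not fit the study drug as described.

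The timing wording raises a second question. A participant who is not about to go to bed at 10 PM cannot follow both descriptions, and nothing says which one applies. That is first a matter of participant safety. It also lets the interval between dose and bed vary without being tracked, and sleep is the mediator in Aim 3.

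**Working it through.** **1. Reminders set against the drug description**

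| Item | E4 reminders | E3 |
|---|---|---|
| Gastric irritation | named | not mentioned |
| Diarrhea medication | named | not mentioned |
| Narcotic medication | named | within CNS depressants |
| Next-day driving at 20 mg | not named | caution to be given |
| Somnolence, impaired alertness | not named | named |

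**2. Where the driving caution would apply.** Assume that week 2 is seven nightly doses starting on the evening of the second Monday; this fits the 14 study days used in the payment section.
- Mornings after a 20 mg dose: 7.
- Of these, lab visits fall on Wednesday, Friday and Monday: 3. Mornings with no visit: 7 − 3 = 4.
- 10 PM dose to 10 AM visit: 12 hours.
- The impairment check is at the end of the visit, so it bears on the journey home. It does not bear on the journey in, or on the 4 mornings without a visit.

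These are exposure days, not counts of drivers. The documents do not give the share who drive.

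**3. Payment.** The plan's figures reproduce: 4 × $2 = $8 per day; $8 × 14 = $112; $10 × 7 = $70; $15 × 7 = $105; $112 + $70 + $105 + $50 = $337.
- Tied to the timed prompt: the text reply, $2 × 14 = $28. That is 28/112 = 25% of compliance pay and 28/337 = 8.3% of the total.
- The bottle, pill-count and riboflavin metrics, $112 − $28 = $84, have no stated time window.

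**4. When the two timing rules agree**

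| Dose | Bed by (+30 min) | Earliest waking: 7 h from dose | Earliest waking: 7 h from latest bedtime |
|---|---|---|---|
| 10:00 PM | 10:30 PM | 5:00 AM | 5:30 AM |
| 10:30 PM (last prompt) | 11:00 PM | 5:30 AM | 6:00 AM |

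The documents give no bedtimes. For assumed bedtimes after a 10 PM dose, the dose-to-bed interval would be 60 minutes (11 PM), 120 minutes (midnight) or 180 minutes (1 AM), against the 30 minutes in E3. The share of participants affected cannot be computed. The 10 AM visit is 12 hours after a 10 PM dose and does not itself breach the 7 hours.

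**The case against.** Much can be said for the plan, and most of it stands as a limit on the point.

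- **Consent.** The consent form is not in the text reviewed. Recruitment and Informed Consent (E4) promises a full account of risks, and Incomplete Disclosure (E10) says that no risk information will be withheld. A reader might infer that participants are never told about driving. The documents do not support that; they show only that the stated reminders do not name it.
- **Completeness.** E4 does not say that its list is exhaustive, so it cannot be read as fixing the whole content of the information.
- **Sedatives, CYP3A inhibitors and alcohol.** A reader might infer that these are neglected. They are not. Any medicine must be reported and narcotics are named. Sedatives are excluded in E1 and CYP3A inhibitors in E4. E10 excludes or reschedules users of CNS-active medication. E4 makes the ban on evening alcohol explicit.
- **Cough medication.** E10 gives over-the-counter use for a cold as an example of CNS-active medication use, so this item has a plausible basis and is not part of the point.
- **Timing.** E3 summarizes the recommended use for insomnia, and a study may set a fixed hour; 10 PM also holds the gap to the 10 AM tests near 12 hours. The two rules agree for anyone in bed by 10:30 PM. A reader might infer that participants are paid throughout to dose by the clock; only the $28 for text replies is linked to the prompt.
- **Origin of the text.** The same part of E4 refers to three experiments, where the parallel paragraph in E10 refers to this project. That is consistent with text carried over from another study, but it remains an inference.

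None of this supplies a source for the two unmatched items, places the E3 driving caution in the stated reminders, or says which timing rule governs.

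**Conclusion.** The point holds in a limited form. Two reminders have no source in the protocol's drug description. The stated reminders do not name a caution that E3 says goes with 20 mg, the dose assigned to the whole active arm in week 2. The expectation that driving will be rare describes most participants and gives no instruction to those who do drive.

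On timing, there is an unreconciled rule, not a contradiction for everyone. With a 10 PM dose it bites for participants who go to bed after 10:30 PM, or who plan to wake before 5:00 to 5:30 AM. How many that is cannot be known from the documents, and no effect on the Aim 3 sleep measure can be quantified.

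The conclusion rests on the text of E3, E4, Study design, Medication compliance and Subject participation requirements. It has no bearing on power, alpha or sample size.

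**What to change.** The investigators should:

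1. Reconcile the participant information in E4 (Other Protections Against Risk) with the drug description in E3.
2. Reconcile the 10 PM rule in Study design, Medication compliance and Subject participation requirements with the bedtime wording in E3, and state in the participant instructions which governs.
3. Summarize the dose-to-bed interval by arm from the wrist-device and sleep-questionnaire data already collected, as far as those records and the medication-bottle records carry clock times.

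The clinical content is for the investigators to settle; no dose, time or clinical rule is proposed here. The cost is a wording amendment, a revised information sheet and one descriptive summary, with no new procedure and no extra participants.

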3. **Sleep interaction:** To characterize the degree to which sleep mediates the effect of suvorexant on drug cue reactivity. We hypothesize an indirect effect of suvorexant on drug cue reactivity via sleep, such that attenuation of cocaine cue reactivity (attentional bias, craving) will be greater in those with larger improvements in sleep duration.

*Conceptual Model:
Orexin System Effects on Relapse Risk*

Figure 1. Summary of Conceptual Model

Research Plan

Our group at the University of Texas Center for Neurobehavioral Research on Addiction (CNRA) has developed, utilized, and validated laboratory models of drug relapse, allowing us to examine pharmacotherapeutic and cognitive-behavioral interventions for relapse prevention.

Study design. To accomplish the project aims, we will utilize a mixed-model experimental design, with a between-groups factor of dose (suvorexant vs. placebo) and a within-subjects factor of time. Subjects will receive suvorexant (**10 mg week 1, 20 mg week 2**) or placebo PO, once daily at 10 PM. Medication condition will be double-blind, with urn-randomized assignment to dose condition balanced by gender and severity of cocaine use. A summary of timelines and measures is shown in the Table below.

Mon	Wed	Fri	Mon	Wed	Fri	Mon
1,4,5,6,7	1,2,3,4,5	1,2,3,4,5	1,2,3,4,5,6,7	1,2,3,4,5	1,2,3,4,5	1,2,3,4,5,6,7
Key: (1) Provide medication (MEMS bottle); (2) Compliance data for medication adherence (MEMS, pill count, riboflavin, text message); (3) Side effects data, med check, UA toxicology; (4) Sleep data; (5) stress /anxiety data; (6) acute stressor challenge (cold pressor); (7) Cue reactivity data						

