Risks for Cold Pressor Test. Individuals with cardiovascular disorders and neurological disorders should not participate. This information will be obtained during medical screening. Due to individual variation in pain and cold sensitivity, for some subjects the cold water may become too painful to sustain immersion for 90 seconds. There are no lasting effects from placing the hand and wrist in ice water (0° Celsius) for 90 seconds.

Risks for Physical Examination. There is a slight risk of bruising and infection in the blood draw procedures. This draw and the intake screening and physical exam are part of the CNRA General Evaluation protocol, and are approved under protocol HSC-MS-05-0322 and detailed therein.

E4. Adequacy of Protection Against Risks

Procedures to Minimize Drug-Related Risks.

We will screen very carefully for alcohol use and depressive symptoms. It will be made explicit that participants are not to drink alcohol in evening. We will use the Alcohol Use Disorders Identification Test (AUDIT) score and our mental health counselors SCID-screeners to enroll only those with low risk for alcohol abuse. Subjects will report no current depressive symptomatology (Beck Depression

Inventory, or BDI < 15), with no past depressive episodes or suicidal ideation. The Columbia Suicide Severity Rating Scale (CSSRS) will be administered at each visit (see additional details below), as per NIH/FDA guidelines. Indication of regular alcohol use by AUDIT score, intake self-report, or breath alcohol, or indication of increase in depressive symptomatology / suicidality as measured by the CSSRS will result in study stopping (see details below). Will exclude for any patients taking CYP3A inhibitors; patients with severe hepatic impairment; and women who are or become pregnant. Pregnancy and drug tests are administered on via urinalysis on lab testing days. Women of childbearing capacity must be taking one form of birth control. We will exclude for women with BMI > 30 to decrease risk of side effects, although it should be noted that in our cocaine use disorder population, we rarely encounter obese patients.

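### The between-visit reporting reminder does not fit brief single events, and the first dose waits 36 h, past a second dose, for a scheduled side-effects check (low severity)

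*Combined protocol and SAP*

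**What the plan says.** **Dosing.** Under Study design, participants take suvorexant (10 mg in week 1, 20 mg in week 2) "or placebo PO, once daily at 10 PM". The night on which 20 mg starts is not named.

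**Visits.** Under Subject participation requirements, "subjects will visit the lab at 10 AM" on Mondays, Wednesdays and Fridays. The longer cue-reactivity visits fall "on each Monday (day 1, 7, and 14").

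**Scheduled safety checks.** In the Study design table, the code for "3) Side effects data, med check, UA toxicology" is absent on the first Monday and present at each of the six later visits. Subject participation requirements lists a side-effects questionnaire at every visit. On the first Monday morning, however, that would precede any dose.

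**Between visits.** The nightly text (Medication compliance) prompts the dose and asks for a one-word confirmation. E4 provides daily monitoring of pill taking, weekly review of adverse events, and medication information that reminds the participant to "notify treatment research clinic nurse or physician of any side effects that persist or worsen".

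**Known risks.** E3 lists sleep-driving and other complex behaviours, impaired alertness, "sleep paralysis, hypnagogic/hypnopompic hallucinations", and a next-day driving caution at 20 mg.

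**Existing protection.** Participants are screened, and on alcohol E4 says "It will be made explicit that participants are not to drink alcohol in evening". Most use public transport, "thus driving hazards are expected to be rare". Visits include a side-effects profile, an impairment battery and a suicidality screen.

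**The concern.** The reminder is framed around effects that last or get worse. Several of the risks in E3 can be single short episodes at night or the next morning. An episode of sleep paralysis or sleep-driving that is over by breakfast meets neither condition, yet staff would want to know of it before the next tablet.

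The schedule adds to this. None of the contacts described between the first dose and the first post-dose visit asks about symptoms. Unless the participant volunteers the event, a second dose is taken before anyone asks. The step to 20 mg can have the same gap, and E3 describes the impairment risk as dose-related.

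What is at stake is the timing of detection for a known class of event. No endpoint, sample size or analysis is affected.

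**Working it through.** The plan states no interval from dose to check, so there is no figure of its own to reproduce. Its payment totals do confirm the counts used below: 14 dosing days x $8 = $112; 7 visits x $10 = $70; 7 visits x $15 = $105; with the $50 bonus, 112 + 70 + 105 + 50 = $337, as stated.

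**Inputs.**
- Doses at 10 PM on 14 nights (Study design; Subject Payment).
- Visits at 10 AM on Mon, Wed, Fri, Mon, Wed, Fri, Mon (Study design table; Subject participation requirements).
- Side-effects code at every visit except the first (Study design table).

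**Inference on the first night.** Medication is handed out on the first Monday. Fourteen nights from that Monday end on the Sunday before the seventh visit, so every paid dose can be verified at a visit. A Tuesday start would put the fourteenth dose after the last visit. The table also shows the medication code on the last Monday. I give that less weight, because a dose that night would be a fifteenth.

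**Day numbering.** The plan labels the Mondays 1, 7 and 14. Counted consecutively they are days 1, 8 and 15. I work from weekdays, so the labels do not affect the result.

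**Gap = next scheduled check minus dose time.**

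| Dose night | Next check | Gap | Further doses before check |
|---|---|---|---|
| Mon | Wed 10 AM | 36 h | 1 |
| Tue | Wed 10 AM | 12 h | 0 |
| Wed | Fri 10 AM | 36 h | 1 |
| Thu | Fri 10 AM | 12 h | 0 |
| Fri | Mon 10 AM | 60 h | 2 |
| Sat | Mon 10 AM | 36 h | 1 |
| Sun | Mon 10 AM | 12 h | 0 |

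One week: 36 + 12 + 36 + 12 + 60 + 36 + 12 = 204 h. Two weeks: 408 h; 408 / 14 = 29.1 h on average, with 6 of 14 doses checked at 12 h.

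**With a query at about 10 AM after the first dose at each level.**
- 20 mg from the second Monday: two gaps fall from 36 h to 12 h. 408 - 2 x 24 = 360 h; 360 / 14 = 25.7 h; 8 of 14 at 12 h.
- 20 mg from the Sunday before or the Tuesday after: that gap is already 12 h, so only the first 10 mg dose gains. 408 - 24 = 384 h; 384 / 14 = 27.4 h; 7 of 14 at 12 h.
- In every case the two Friday gaps (60 h) and two Saturday gaps (36 h) are unchanged.

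**The reminder against the risk list.** E4 names effects that last or worsen. E3 names events that can be single and brief. The two do not match, and this holds whatever the start night.

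**The case against.** The case for leaving the plan alone is respectable. The drug is approved, 10 mg is the recommended dose, and E10 keeps all doses within the prescribed range. Participants are seen three times a week. E10 takes a full side-effects profile at each visit, with no restriction to lasting effects. The Adverse Event Log takes any event. E4 says that any abnormal event is evaluated and can lead to removal, and that physicians can be paged during the day. No stated requirement is breached. All of this stands, and it is why the point is minor. It does not remove the mismatch, because between visits staff can act only on what they are told.

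A reader might infer three stronger things that the documents do not support.

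- **That the plan asks only for lasting or worsening effects.** E4 lists what the medication information will remind participants to do and does not say that the list is exhaustive. The consent and information sheets are not in this copy and may ask for more. Nor can a missing after-hours contact be claimed.
- **That brief events go unrecorded.** They can be captured at the next visit. The consequence is delay, with one more dose after a Monday-night first dose if the participant does not call.
- **That a stated number of participants would be spared harm.** The documents give no event rate. Even an assumed rate would count events, not the benefit of asking. That benefit also depends on whether the participant would otherwise have called, would answer the query, and would have the dose held.

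**Conclusion.** The point holds as a low-severity, inexpensive improvement. The reminder set out in E4 does not fit the brief single events in E3. The first 10 mg dose has no scheduled post-dose check for 36 h, with one further dose in between. The same is true of the first 20 mg dose if it is taken on the second Monday night, the natural reading of a week 2 start.

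The 36 h figure rests on a Monday-night first dose, which is inferred from 14 dosing days and seven visits. The mismatch in wording does not depend on that inference, but it is subject to what the unseen sheets say.

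The optional text shortens one or two gaps by 24 h each and leaves the longest ones, at weekends, as they are. The rewording applies on every night, so it is the more useful of the two changes. The size of the benefit cannot be estimated from the documents.

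**What to change.** **Main change.** Reword the reminder in E4, and match it in the information sheet if that does not already say so. Participants should report any single episode of sleep-driving or other complex behaviour, sleep paralysis, hallucination or next-day impairment to the nurse or physician before taking the next dose. Add that the study physician, still blinded, decides whether that dose is held. A physician-directed hold should not cost the participant compliance payment; otherwise up to $8 a day (4 metrics x $2) rewards taking the tablet. Record such holds separately from missed doses.

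**Clarification.** Name the night on which 20 mg starts.

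**Optional addition.** Send a short symptom query through the existing text service the morning after the first dose at each level. The existing nurse reviews it the same day, calls anyone who does not reply, and enters events in the Adverse Event Log. If the service cannot take symptom replies, use a brief nurse call.

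**Cost.** An IRB amendment for the wording and procedure. The queries number 2 x 30 = 60 for completers or 2 x 45 = 90 if all enrolled are texted; at 3 to 4 enrolled a month that is 6 to 8 a month. Add a few minutes of nurse time, occasional calls, and possibly more recorded events. Visits, sample size and planned analyses do not change; dosing changes only if the physician holds a dose.
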